## 2 SCHEDULE OF ASSESSMENTS (SoA)

**Table 3: Schedule of Assessments**

Evaluation or Procedure	Screening Period	Treatment Period (Cycle = 28 days)												Follow-Up Period
	Screening ≤28 Days prior to D1	Cycle 1			Cycle 2		Cycle 3		Cycle 4-12	Cycle 12	Cycle 13 onwards	End of Treatment Visit (EOT) 	90-Day Safety Follow-up Visit/ End of Study Visit 	
Day	Screen	D1	D4 ±1 day	D8 ±1 day	D15 ±1 day	D1 ±1 day	D15 ±1 day	D1 ±1 day	D15 ±1 day	D1 ±2 days	D28 ±2 days	D1 ±2 days	Within 14 days after decision on treatment discontinuation	±7 days
Starting Evaluations and Eligibility														
Informed consent	X													
Inclusion/exclusion criteria	X	X 												
Demography	X													
Medical history/current medical condition	X													
Disease history/staging/Ann Arbor	X													
Disease risk assessment (IPI)	X													
Throughout Evaluations														
Prior/concomitant therapy 	X	X	X	X	X	X	X	X	X	X		X	X	X
Physical examination (F – full, L – limited)	F	L						L		L 		L 	F	
ECOG performance status	X	X 				X		X		X			X	
Body weight/height 		X	X	X	X	X	X	X	X	X		X	X	
B-symptoms	X	X				X		X		X		X	X	
Vital signs 	X	X	X	X	X	X	X	X	X	X		X	X	
12-lead resting ECG	X	X 			X 	X 		X 		X 5a			X	
Adverse events (AEs, SAEs and AESIs)	X	X	X	X	X	X	X	X	X	X		X	X	X
Laboratory														
Urinalysis (local lab)	X	X				X		X		X			X	
Pregnancy test (FCBP) 	X	X 		X 	X 	X 		X 		X 		X 	X	
Pregnancy and risks counselling	X	X				X		X		X			X	
US only: pregnancy and risk interview	X	X				X		X		X			X	
Hematology and Serum chemistry (local lab) 	X	X	X	X	X	X	X	X	X	X		X	X	
Serology Hepatitis B (local lab)	X													

Evaluation or Procedure	Screening Period	Treatment Period (Cycle = 28 days)												Follow-Up Period
	Screening ≤28 Days prior to D1	Cycle 1				Cycle 2		Cycle 3		Cycle 4-12	Cycle 12	Cycle 13 onwards	End of Treatment Visit (EOT) 	90-Day Safety Follow-up Visit/ End of Study Visit 
Day	Screen	D1	D4 ±1 day	D8 ±1 day	D15 ±1 day	D1 ±1 day	D15 ±1 day	D1 ±1 day	D15 ±1 day	D1 ±2 days	D28 ±2 days	D1 ±2 days	Within 14 days after decision on treatment discontinuation	±7 days

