Serology Hepatitis B, DNA, if indicated (local lab)	X 					X 		X 		X 			X 	
Serology Hepatitis C (local lab)	X													
Coagulation (aPTT or PTT, PT and/or INR) (local)	X									C4D1			X	
Thyroid Stimulating Hormone (TSH-local lab) 	X									C4D1			X	
Tafasitamab ADAs		X 				X 		X 		X  ,	X 		X 	
PK tafasitamab		X 	X 	X 	X 	X 	X 	X 	X 	X 10a ,	X 		X 	
CD19 expression 	X													
Imaging and Tumor Evaluation														
PET-CT or PET-MRI	X										X 	X 	X 	
CT or MRI								X 11a		X 11a		X 11a		
Biopsy/Tissue														
Tissue sample collection for central pathology review	X													
Bone marrow aspiration & biopsy	X 								X 	X 	X 	X 		
Drug Administration														
LEN capsules allocation (Incl. patient home intake record)		X				X		X		X				

Abbreviations: AE=adverse event; ADA=Anti-drug antibodies; AESIs=adverse events of special interest; aPTT= activated partial thromboplastin time; anti-HBc=hepatitis B core antibody; β-HCG=beta-human chorionic gonadotropin; C=cycle; CT=computed tomography; D=day; ECG=electrocardiogram; ECOG=Eastern Cooperative Oncology Group; eCRF=electronic case report form; EOS=end of study; EOT=end of treatment; F=full physical examination; FCBP=female of childbearing potential; HBV=hepatitis B virus; INR=international normalized ratio; IP=International Prognostic Index; IRRs=infusion-related reactions; L=limited physical examination; LEN=lenalidomide; MRI=magnetic resonance imaging; PE=physical examination; PET=positron emission tomography; PK=pharmacokinetics; PT=prothrombin time; PTT=partial thromboplastin time; SAE=serious adverse event TSH=Thyroid stimulating hormone

Before study treatment administration.

Previous/Concomitant therapy will be recorded as per [Section 7.8](#). After disease progression only anticancer treatments and other relevant concomitant medications, i.e., used for treatment of an AE (at the discretion of the investigator) should be entered.

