A limited PE (L) will be performed on Day 1 of every other Cycle, e.g., Cycle 5, Cycle 7, Cycle 9, Cycle 11. From Cycle 13 onwards, a limited PE will only be performed at the discretion of the investigator if directed by any clinical symptoms or adverse events.

Body height will be measured at Cycle 1 Day 1 only. Body weight can be measured up to 24 hours prior to the study treatment administration.

12-lead resting ECG performed within 3 hours after the end of tafasitamab infusion.

5aA 12-lead resting ECG will be performed (within 3 hours after the end of tafasitamab infusion.) on D1 of every third cycle until Cycle 12, i.e., Cycle 6, Cycle 9 and Cycle 12.

Pregnancy tests: A serum ( $\beta$ -HCG)/urine pregnancy test is mandatory only for females of childbearing potential (FCBP). A serum pregnancy test will be performed locally at Screening and at the End of treatment visit. At all other indicated time points, a urine pregnancy test for FCBP will be performed locally and the result must be negative for dosing. At Cycle 1 Day 1 pregnancy test must be performed within 24 hours prior to the start of study treatment. For US only, a pregnancy test at screening must be performed within 10 to 14 days prior to the start of study treatment. For US FCBP with irregular menstrual cycle a urine pregnancy test will be performed every two weeks. A home urine pregnancy test kit and the home urine pregnancy test diary will be handed out to the US FCBP with irregular menstrual cycle on Cycle 2 Day1 to Cycle 12 Day1. Pregnancy testing and counseling must be performed if a patient misses her period or if there is any abnormality in her menstrual bleeding. Lenalidomide treatment must be discontinued during this evaluation. Patients reaching end of treatment during Cycle 1 – Cycle 12 a serum pregnancy test will be performed at-least 4 weeks after the last dose of study drug, in accordance with the Lenalidomide SmPC/USPI.

Sample to be collected and evaluated in the local laboratory (can be done on the day before study treatment administration) and reviewed by study treating physician before study treatment administration.

HBV-DNA to be measured at screening and re-measured at subsequent visits only if anti-HBc was positive at screening.

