#### **9.4.4 Viral Serology**

Patients will be examined locally according to the schedule in [Section 2](#) for viral hepatitis B and hepatitis C.

Hepatitis B biomarkers include hepatitis B surface antigen (HBsAg), total anti-hepatitis B core antibody (HBcAb) and anti-hepatitis B surface antibody (anti-HBsAb). Patients with a positive test for anti-HBc can only be included if hepatitis B virus (HBV) deoxyribonucleic acid (DNA) is not detected. **In these patients only**, HBV DNA should be assessed at various subsequent visits as outlined in [Section 2](#).

In the context of exclusion criteria, seropositive for or active viral infection with HBV means:

- HBsAg positive
- HBsAg negative, anti-HBs positive and/or anti-HBc positive and detectable HBV DNA

**Note:** Patients who are HBsAg negative, anti-HBc positive and HBV DNA negative are eligible.

**Note:** Patients who exhibit the classical vaccination profile of anti-HBs positive, anti-HBc negative, and HBsAg negative are eligible.

If HBV DNA becomes detectable during treatment, patients should be prophylactically treated and followed-up for potential hepatitis B reactivation. If the HBV-DNA assay is positive, then patients can only stay in the study if they are assessed by a physician experienced in the treatment of hepatitis B and pre-emptive treatment is initiated, if deemed appropriate, and/or according to local practice/guidelines.

**Hepatitis C serology is to be done at screening only.** Hepatitis C biomarkers include anti-hepatitis C virus (HCV) antibody. For patients who are positive for anti-HCV antibody, HCV-ribonucleic acid (RNA) should be measured. A positive Hepatitis C test is defined as a positive test for HCV antibodies **and** a positive test for HCV RNA.

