## 12.8 Appendix 8: Hepatitis Virus Serology

Patients will be examined according to the **SoA** for viral hepatitis B and C serology. Hepatitis B biomarkers include hepatitis B surface antigen (HBsAg), total anti-hepatitis B core antibody (anti-HBc) and anti-hepatitis B surface antibody (anti-HBsAb). Patients with a positive test for anti-HBc can only be included if HBV DNA is not detected. **In these patients only**, HBV DNA should be assessed at various subsequent visits as outlined in the **SoA**.

In the context of exclusion criteria, seropositive for or active viral infection with HBV means:

- HBV surface antigen positive
- HBV surface antigen negative, HBV surface antibody positive and/or HBV core antibody positive and detectable viral DNA. Note: Patients who are HBV surface antigen negative and viral DNA negative are eligible
- Patients who exhibit the classical vaccination profile of HBV surface antibody positive, HBV core antibody negative, and HBV surface antigen negative are eligible

If HBV-DNA becomes detectable during treatment, patients should be prophylactically treated and followed-up for potential hepatitis B reactivation as per local medical practice or institutional guidelines for CD20 antibodies such as RTX. If the HBV-DNA assay is positive, then patients can only stay in the study if they are assessed by a physician experienced in the treatment of hepatitis B and pre-emptive treatment is initiated, if deemed appropriate, and/or according to local practice/guidelines.

**Hepatitis C serology is to be done at screening only.** Hepatitis C biomarkers include anti-HCV antibody. For patients who are positive for anti-HCV antibody, HCV-RNA should be measured.

A positive Hepatitis C test is defined as a positive test for HCV antibodies and a positive test for HCV RNA.

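### No HBV-DNA test is scheduled between Cycle 12 Day 1 and end of treatment for anti-HBc-positive patients, although tafasitamab and the DNA-triggered action rule both continue

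*Protocol*

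**What the plan says.** **Who may enrol.** Protocol Section 9.4.4 (Viral Serology) states: "Patients who are HBsAg negative, anti-HBc positive and HBV DNA negative are eligible".

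**What happens on a positive result.** Section 9.4.4 continues: "If HBV DNA becomes detectable during treatment, patients should be prophylactically treated and followed-up for potential hepatitis B reactivation". Section 9.4.4 and Appendix 8 (Section 12.8) also make staying in the study conditional: "If the HBV-DNA assay is positive, then patients can only stay in the study if they are assessed by a physician". That physician must be experienced in treating hepatitis B. Pre-emptive treatment is then started where judged appropriate or as local practice dictates.

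**When the test is done.** Section 9.4.4 sets no times. It says "HBV DNA should be assessed at various subsequent visits as outlined in" Section 2, and Appendix 8 also points to the schedule. In Table 3 the row "Serology Hepatitis B, DNA, if indicated (local lab" is marked at Screening, C2D1, C3D1, Day 1 of Cycles 4-12 and EOT. The C12D28, Cycle 13 onwards and 90-day follow-up cells are blank. Footnote 8 reads: "HBV-DNA to be measured at screening and re-measured at subsequent visits only if anti-HBc was positive at screening". It limits who is re-tested and names no cycle.

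**How long treatment lasts.** Under the Synopsis and Section 5.1, lenalidomide (LEN) stops after at most 12 cycles. Tafasitamab continues alone until progression, unacceptable toxicity, withdrawal, death or loss to follow-up.

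**The concern.** The protocol admits a group at risk of hepatitis B reactivation, lists reactivation as an adverse event of special interest (AESI, Section 9.4.7.4), and bases its pre-emptive rule on one laboratory result. It schedules that test on Day 1 of every cycle from Cycle 2 to Cycle 12, then not again until EOT, while the same antibody continues and the rule still applies.

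Other safety measures continue after Cycle 12, but they act mainly on enzyme rises or symptoms. A reactivation that shows itself in those ways need not wait until EOT to be found. A patient whose DNA becomes detectable before any enzyme rise or symptom could go unnoticed until EOT, so antiviral treatment and the specialist assessment could start late. The issue is patient safety. No endpoint, analysis set or design figure depends on it.

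**Working it through.** **1. Is the blank cell real?** Table 3 has 14 visit columns: Screening; C1D1, D4, D8 and D15; C2D1 and D15; C3D1 and D15; Cycle 4-12 D1; C12D28; Cycle 13 onwards D1; EOT; and 90-day follow-up. The HBV-DNA row has all 14 cells, so no cell was lost in text extraction. The rows for adverse events, pregnancy test and "Hematology and Serum chemistry (local lab" also have 14 cells and are marked at Cycle 13 onwards, which confirms the alignment.

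**2. Does other text fill the cell?** Section 9.4.4 and Appendix 8 defer to the schedule, and footnote 8 qualifies only the cells that carry its mark. A site might read its phrase about later visits loosely, but nothing in it names Cycle 13 or beyond. The marked cells therefore govern.

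**3. Length of the gap.** Cycles last 28 days and a month is 30.4375 days (SAP Section 4.3.3).

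- C12D1 is study day 1 + 11 × 28 = 309, which is 308 days after C1D1.
- Stopping at the end of Cycle 24: 24 × 28 = day 672. The gap is 672 − 309 = 363 days, and 363 / 30.4375 = 11.9 months. It spans 12 Day 1 visits (C13 to C24).
- Treated for 3 years: 3 × 365.25 = 1,095.75 days. The gap is 1,095.75 − 308 = 787.75, about 788 days, and 787.75 / 30.4375 = 25.9 months.

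Three years is the minimum follow-up for patients still on treatment at end of study, so an early enrollee could have a longer gap. The documents do not say how many patients will reach either point.

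**4. How many patients.** Planned enrolment is about 51. The documents give no anti-HBc prevalence, so 5-15% is assumed. In L-MIND (Section 3.3.2), 34 of 80 patients (42.5%) entered monotherapy. That share can include patients who stopped LEN before Cycle 12, so half of it (21.25%) is also shown. With *p* = prevalence × share, the expected number is 51*p*, and the chance that nobody is exposed is (1 − *p*)^51, treating patients as independent.

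| Prevalence | Share reaching Cycle 13 | *p* | Expected exposed | Chance of none |
|---|---|---|---|---|
| 5% | 42.5% | 0.02125 | 1.08 | 0.334 |
| 15% | 42.5% | 0.06375 | 3.25 | 0.035 |
| 5% | 21.25% | 0.010625 | 0.54 | 0.580 |
| 15% | 21.25% | 0.031875 | 1.63 | 0.192 |

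These figures count patients who enter the gap, not patients who reactivate. The documents give no basis for a reactivation rate.

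**The case against.** **The blank may be deliberate.** Other on-treatment items also lose their mark at Cycle 13, including ECOG status and "Urinalysis (local lab", and the change coincides with the end of LEN. No section says DNA must be tested throughout treatment, so no two sections contradict each other. This stands: the documents do not show intent, and the point concerns a design choice. But several other reductions are spelled out in footnotes (limited physical examination, ECG, ADA and PK sampling), and footnote 8 states no stopping point.

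**Safeguards remain.** These are:

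- chemistry, including ALT, AST and bilirubin, on Day 1 of each cycle and reviewed before dosing (Table 3, footnote 7);
- no new cycle while treatment-related toxicity exceeds Grade 2 (Section 7.3.3);
- repeats of clinically significant abnormal results, and optional extra tests (Section 9.4.5);
- institutional infection prophylaxis for high-risk patients (Section 7.9, Appendix 7);
- AESI reporting within 24 hours (Section 9.4.7.1).

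They reduce the risk, but none requires a DNA test. Table 15's row for other non-hematologic events of Grade 3 or higher helps less than it seems. Its only mandatory action is to interrupt LEN, which has ended by Cycle 13, and it lets tafasitamab continue if clinically appropriate.

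**Local practice governs hepatitis B care.** Section 9.4.4 and Appendix 8 refer to local guidelines, and sites may go on testing anyway. Those clauses apply once DNA has been detected, however, and they do not schedule the test that detects it.

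**The numbers are small and the harm is not quantified.** This also stands, and it limits the weight of the point without removing it.

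**Conclusion.** The concern holds. Followed as written, the schedule leaves about 363 days (to the end of Cycle 24) to about 788 days (3 years) without an HBV-DNA test in anti-HBc-positive patients who stay on tafasitamab, while the rule that depends on that test continues.

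The gap follows directly from the schedule. The clinical consequence is less certain. On the assumed prevalence and the L-MIND share, about 1 to 3 of 51 patients would be exposed, with a 33% to 3% chance of none. At half that share it is about 0.5 to 1.6 patients, with a 58% to 19% chance of none. It should be corrected as a cheap patient-safety improvement. It does not affect the validity of any analysis.

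**What to change.** Mark the Cycle 13 onwards Day 1 cell of the HBV-DNA row for anti-HBc-positive patients, and state the interval in footnote 8: at least every third cycle (C13, C16, C19 and so on) until EOT.

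The documents recommend no HBV-DNA interval, so every third cycle (3 × 28 = 84 days) is a proposal. It roughly matches the 3-month scan interval in footnote 11a for Cycles 13-24. From Cycle 25 scans become yearly, so beyond that point the interval rests on the safety argument alone. The longest on-treatment stretch without a scheduled test falls from 363 or about 788 days to 84. For a patient stopping at the end of Cycle 24, the last test is at C22D1 (day 1 + 21 × 28 = 589), which is 672 − 589 = 83 days before the end of that cycle.

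If the blank is deliberate, footnote 8 should say so and require a DNA test whenever transaminases rise.

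**Cost.** One schedule cell and one footnote line, plus a local assay on blood already drawn on Day 1. That is 4 assays per patient to the end of Cycle 24 (C13, C16, C19, C22) and at most 10 per patient treated for 3 years (C13 to C40; C40D1 is 39 × 28 = 1,092 days after C1D1). No extra visit or procedure is needed.

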## 3 INTRODUCTION

### 3.1 Study Rationale

#### 3.1.1 Disease Overview

DLBCL is the most common type of non-Hodgkin lymphoma (NHL), representing approximately 30-40% of all NHLs with a median age at diagnosis of 64 years. DLBCL is an aggressive B-NHL and the majority of patients present with advanced disease. DLBCL is increasingly recognized as a heterogeneous disorder disease with distinct molecular subtypes ([Lenz \*et al.\*, 2008](#); [Flowers \*et al.\*, 2010](#); [Vaidya and Witzig, 2014](#); [Schmitz \*et al.\*, 2018](#)).

Standard treatment for patients with newly diagnosed DLBCL consists of immuno-chemotherapy with the anti-CD20 monoclonal antibody (mAb), RTX, and CHOP administered for 6-8 cycles (R-CHOP) ([Tilly \*et al.\*, 2015](#)). The addition of RTX has substantially improved the results of CHOP-chemotherapy, yielding complete and sustained remission in about 60% of cases ([Coiffier \*et al.\*, 2002](#)). But still approximately 30–40% of patients ultimately will relapse and are not cured by first-line therapy with R-CHOP, and approximately 10% of patients are refractory to R-CHOP as first-line therapy (primary refractory) ([Coiffier \*et al.\*, 2010](#)).

In patients progressing or relapsing after first-line treatment, the main consideration for further treatment is whether the patient is a candidate for HDT and ASCT. Salvage chemotherapy followed by HDT and ASCT is standard treatment for transplant-eligible patients and may offer a second chance of cure for about 30–40% of the patients ([Crump \*et al.\*, 2017](#); [Gisselbrecht \*et al.\*, 2010](#)). However, the majority of R/R DLBCL patients are ineligible for ASCT due to comorbidities and older age. Despite recent advances, the treatment options for patients who have relapsed or progressed after second-line treatment of DLBCL, or who are not eligible for ASCT remain limited.

On 31 JUL 2020, the U.S. Food and Drug Administration (FDA) approved tafasitamab-cxix (Monjuvi®) in combination with lenalidomide for the treatment of adult patients with R/R DLBCL not otherwise specified, including DLBCL arising from low grade lymphoma, and who are not eligible for autologous stem cell transplant. Furthermore tafasitamab (Minjuvi®) was granted conditional approval in R/R DLBCL in Europe on 26 AUG 2021, and thereafter in other countries (e.g., Israel, South Korea).

As per Monjuvi® United States prescribing information (USPI) ([Monjuvi® 2021](#)) and Minjuvi® Summary of product characteristics (SmPC) ([Minjuvi® 2024](#)) the recommended dose of tafasitamab is 12 mg/kg, administered as intravenous (i.v.) infusion. The current approved dosing regimen of tafasitamab in combination with LEN until disease progression or unacceptable toxicity is presented in [Table 4](#).

[figure not shown]
**Table 4: Tafasitamab in Combination With LEN Dosing Regimen as per Monjuvi® USPI in R/R DLBCL**

Currently approved dosing regimen per Monjuvi® USPI			
Drug	Route	Dose	Dosing Schedule 
Tafasitamab	i.v.	12 mg/kg	Cycle 1: Days 1, 4, 8, 15, and 22
			Cycle 2 to 3: Days 1, 8, 15, and 22
			Cycle 4 and beyond: Days 1 and 15
LEN	Oral (capsule)	25 mg	Cycle 1–12: 25 mg on Days 1-21 of each cycle Administer LEN for a maximum of 12 cycles and then continue tafasitamab as monotherapy until progression or unacceptable toxicity

Abbreviations: DLBCL=diffuse large B-cell lymphoma; i.v.=intravenous; LEN=lenalidomide; R/R=relapsed/refractory; USPI=United States Prescribing Information.

Each treatment cycle is 28 days.

**3.1.2 Study Treatment**

As tafasitamab [redacted]  
[redacted] tafasitamab [redacted]  
[redacted] in R/R DLBCL patients.

### 3.2 Non-Clinical Background Information

Tafasitamab is an Fc-modified mAb targeting CD19, a crucial component of B-cell receptor signaling. CD19 is expressed throughout normal B-cell development until terminal plasma cell differentiation and is also present on the surface of malignant hematopoietic cell. Tafasitamab possesses significantly increased tumor cytotoxicity when compared with the parental, non-engineered, murine 4G7 CD19 antibody. The increased binding of tafasitamab to Fc gamma receptors (FcγR), due to the engineered mutations, significantly enhances in vitro antibody-dependent cell-mediated cytotoxicity (ADCC), antibody-dependent cell-mediated phagocytosis (ADCP), and its direct cytotoxic effects (apoptosis) on the tumor cells compared with the non-engineered parental murine antibody ([Lazar et al., 2006](#)).

Non-clinical studies with tafasitamab were designed to support human clinical trials with tafasitamab for the treatment of CD19 positive hematologic malignancies, such as chronic lymphocytic leukemia (CLL), acute lymphoblastic leukemia (ALL) and NHL.

Non-clinical studies evaluating the PK, pharmacodynamics and toxicity of tafasitamab were performed in cynomolgus monkeys. Overall, the findings in five preclinical studies were limited to the expected pharmacological effects of tafasitamab, with no reports of unanticipated toxicity.

More specifically, in the pivotal GLP-compliant, repeat-dose toxicity study, i.v. one-hour infusion of tafasitamab into sexually mature male and female cynomolgus monkeys at doses of 0, 10, 30, and 100 mg/kg once a week for 13 weeks was well-tolerated up to the highest dose tested (with no adverse effects observed) and did not affect safety pharmacology or reproductive endpoints. No mortalities occurred. There were no drug-related effects on body weights, food consumption, clinical signs, neurobehavioral observations, blood pressure, electrocardiography, respiratory rate,

ophthalmology, urinalysis, coagulation, serum chemistry or cytokine analysis. Local tolerance was assessed following each i.v. infusion and did not reveal any adverse effects at the administration sites. The reduced peripheral B-cell counts as well as the histopathological changes to several lymphatic organs (decreased cellularity of the germinal centers in lymphoid follicles of spleen, mesenteric and mandibular lymph nodes) are considered exaggerated pharmacodynamic effects. The no observed adverse effect level (NOAEL) was determined at the highest dose tested (i.e., 100 mg/kg i.v. weekly [QW]) (report MOR208P008).

Following i.v. administration in cynomolgus monkey at dose levels from 0.3-100 mg/kg, tafasitamab exhibited a typical 2-compartment profile. Tafasitamab showed consistent PK parameters across studies and study groups (volume of distribution at steady state [ $V_{ss}$ ] of 52.6-124.3 mL/kg; clearance [CL] of 4.31-7.37 mL/day/kg; mean terminal elimination half-life of 7.7-14.2 days). Dose linearity was observed between 2-100 mg/kg.

